6.2 IMPORTANT PROTOCOL DEVIATIONS

Each protocol deviation must be assessed to determine whether it is an important Protocol Deviation (iPD). The documentation of the iPD categories and how to handle iPDs in the analysis are done in the DV domain.

Handling of iPDs in analysis is included in the DV domain specifications and stored within the TMF in EDMS.

The decision about which protocol deviation (PD) could generate exclusion from analysis sets will be taken during the course of the study and finalised at the last report planning meeting (RPM), i.e. before unblinding.

6.3 INTERCURRENT EVENTS

Not applicable as described in Section 4.

6.4 SUBJECT SETS ANALYSED

The subject sets will be used as defined in the CTP, Section 7.2.1. These include the Enrolled set (ES), Randomised set (RS), Treated set (TS) and Full analysis set (FAS). In addition, the following subject sets for the analysis of PK parameters and biomarkers will be used.

- Screened set (SCR) this analysis set includes all patients having signed informed consent. The SCR will be used for analyses of patient disposition
- PK parameter analysis set (PKS): This set includes all subjects in the treated set (TS) who provide at least one PK endpoint that was not excluded due to a protocol deviation relevant to the evaluation of PK or due to PK non-evaluability (as specified in the following subsection 'Pharmacokinetics'). Thus, a subject will be included in the PKS, even if he/she contributes only one PK parameter value to the statistical assessment. Descriptive analyses of PK parameters will be based on the PKS.
- Biomarker set (BMS): This set includes all subjects from the Treated Set (TS) who provide at least one evaluable measurement assessing the liver or spleen stiffness using FibroScan® or an exploratory biomarker (refer to CTP Section 5.4), that was not excluded due to a protocol deviation relevant to the evaluation of biomarkers.

The discussion on all exceptional cases and problems and the decisions on the allocation of patients to populations will be made at latest at the DBLM.

In Table 6.4: 1 the subject sets which are to be used for each class of endpoint are illustrated.

Page 14 of 33

c43185880-01

Proprietary confidential information © 2024 Boehringer Ingelheim International GmbH or one or more of its affiliated companies.

			Su	ıbject set		
Class of endpoint	SCR	RS	TS	FAS	PKS	BMS
Disposition	Х					
Primary endpoint				X^*		
Secondary efficacy and further efficacy endpoints				X^*		
Secondary and further safety endpoints (including liver decompensation) & treatment exposure			х			
Demographic/baseline endpoints		Х				
Further PK endpoints					Х	
Further biomarker endpoints						Х

Table 6.4: 1 Subject sets analyzed

* Planned analysis around HVPG data in the CTP will not be performed, as described in Section 4.

Handling of Treatment Misallocations in Analysis Sets

If a patient was administered incorrect treatment during the study, for efficacy analyses:

- subjects who took incorrect treatment will be reported under their randomized treatment group. In the case of stratification error at randomisation, the subjects will be analyzed according to the stratum to which they actually belong to (regardless of any mis-assignment to treatment based on identification of the wrong stratum from IRT), as such an error occurs before randomisation and is therefore consistent with regulatory guidance.

If a patient was administered incorrect treatment during the study, then for safety the following will be used in addition:

- If a patient is planned to receive Avenciguat, then patients will be reported under the planned treatment from the randomisation visit for safety analyses because the overall safety profile is expected to be driven by the amount of drug received in totality over the entire treatment duration. It is not expected that the safety profile will deviate from the planned treatment regimen if the subject receives only one or two kits of the incorrect medication at only some dosing occasions.
- If a patient is planned to receive Placebo, then patients will be reported under their randomised treatment group for safety analysis if the patient was administered no Avenciguat kits at any visit. If the patient was administered at least one kit of BI

66-0055 c43185880-01 Proprietary confidential information © 2024 Boehringer Ingelheim International GmbH or one or more of its affiliated companies.

685509 during the treatment period, then the patient will be assigned to Avenciguat treatment group.

6.6 HANDLING OF MISSING DATA AND OUTLIERS

6.6.1 Efficacy data

No imputation of missing data is planned for the efficacy endpoints.

6.6.2 Safety data

Missing safety data will not be imputed.

An analysis of the changes from baseline to the last available value under treatment and the minimum and maximum post baseline will be determined for quantitative safety laboratory variables.

6.6.3 Missing dates and times

Missing or incomplete AE dates are imputed according to BI standards (9.2).

If the date of first drug administration is missing but the patient was randomised, the date of the first drug administration will be set to the date of randomisation. If the date of first administration is partially missing with the month and year present, the day will be set to the date of randomisation if randomisation was in the same month. If randomisation was in the month prior to the first drug administration the missing day will be imputed as the first day of the month.

Partial start and stop dates for concomitant therapies will be imputed to enable subsequent calculation (but not for display) by the following "worst case" approach:

- If the day of the end date is missing, then the end date is set to last day of the month (or to the patient's trial completion date, whichever is earlier).
- If the day and month of the end date are missing, then the end date is set to 31st of December of the year (or to the patient's trial completion date if it is earlier than 31st December of the year).
- If the day of the start date is missing, then the start date is set to first day of the month.
- If the day and month of the start date are missing, then the start date is set to 1st January of the year.

All other cases need to be assessed by the trial team on an individual basis, using above points as guidance.

Proprietary confidential information © 2024 Boehringer Ingelheim International GmbH or one or more of its affiliated companies.

6.6.4 Time since first diagnosis

For incomplete information on the date of the first diagnosis of cirrhosis, time since first diagnosis will be calculated as follows:

- If the year of first diagnosis is unknown, then the time since diagnosis will be set to missing.
- If day and month of the first diagnosis are unknown, time since first diagnosis will be calculated as if diagnosed on the 30th June of that year.
- If only the day of the first diagnosis is unknown, time since diagnosis will calculated as if diagnosed on the 15th of that month.

6.6.5 PK data

Missing data of PK data are handled according to BI standards (9.4).

6.6.6 Biomarker data

For disease specific protein markers (refer to CTP Section 5.4) the following handling of data below or above the limit of quantification will be applied:

- BLQ data will be replaced by 0.5 · LLOQ. Hereby LLOQ will be the maximum used lower reference limit for classification of BLQs. All values lower than LLOQ will be imputed (regardless of whether they are classified as BLQ or not).
- ALQ data will be replaced by ULOQ, if ULOQs are available and are greater than observed study values (i.e. the highest solution was applied for the measurement). Otherwise, ALQ data will be excluded from the analysis.

Otherwise, missing data (NOS - no sample, NOR - no valid result, NOA - not analysed) will not be imputed.

The handling of other biomarkers (e.g. genetic variants in disease genes) will be given in a separate biomarker SAP.

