#### 7.2.5 Further objective analyses

Only descriptive statistics will be presented for further endpoints (defined in Section 2.2.2).

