7.9.2 Biomarker analyses

For all the biomarkers defined in Section 5.4.7, descriptive statistics will be presented.

In detail, for each marker the observed value will be analysed for the BMS via mean, standard deviation, median, Q1, Q3, normalized IQR (0.7413*IQR), minimum, maximum and gMean.

Other exploratory biomarkers may be reported in a separate biomarker report.

c43185880-01

Proprietary confidential information © 2024 Boehringer Ingelheim International GmbH or one or more of its affiliated companies.

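### SAP 6.6.6 can delete biomarker results above the quantification limit but never those below it, so the planned summaries are biased low in expectation

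*SAP*

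**What the plan says.** SAP 6.6.6 limits the rule to one class of marker: "For disease specific protein markers (refer to CTP Section 5.4) the following handling of data below or above the limit of quantification will be applied". Other biomarkers are left to a separate plan.

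- **Low end.** "BLQ data will be replaced by 0.5 · LLOQ". The LLOQ is the largest one used, and "All values lower than LLOQ will be imputed (regardless of whether they are classified as BLQ or not"). Nothing at this end is dropped.
- **High end.** "ALQ data will be replaced by ULOQ, if ULOQs are available and are greater than observed study values". A parenthesis ties this condition to the solution used for the measurement. If the condition fails: "Otherwise, ALQ data will be excluded from the analysis".

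Samples with no material, no valid result or no analysis are dealt with separately and stay missing.

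SAP 7.9.2 then summarises each marker in the biomarker set "via mean, standard deviation, median, Q1, Q3, normalized IQR (0.7413*IQR), minimum, maximum and gMean". Neither section plans a count of excluded ALQ results or a sensitivity analysis. Protocol 7.2.5 sets the level of evidence: "Only descriptive statistics will be presented for further endpoints". SAP Section 4 withdraws the HVPG analyses and the reporting of intercurrent events, but not the biomarker summaries.

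**The concern.** An ALQ result is not missing in the ordinary sense, because it is known to exceed a limit. The fallback treats it like a sample that was never taken, and the trigger is the height of the value itself. The low end has no such branch, so the loss runs in one direction.

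The rule also works visit by visit. A participant whose marker rises above the limit on treatment can be in the baseline summary and absent from a later one. Because SAP Section 7 defines N as the number of non-missing values, the table would show a smaller N but not that the absent values were high. Location statistics, upper quartile and maximum are all exposed.

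**Working it through.** The documents state no figure on this point, so there is nothing to reproduce. The sizes below rest on assumptions.

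**When exclusion applies.** (a) A ULOQ exists but is not greater than the observed study values, for example because other samples were diluted further and quantified above it. Some high values are then lost and others stay. (b) No ULOQ is available. All ALQ values are then lost. With a single usable ULOQ above all quantified values, the SAP substitutes it and nothing is lost.

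**Inputs (all assumed).** Log-normal marker with log-SD s. A fraction p = 0.10 lies above the limit, so z = 1.2816 and φ(z) = 0.1755. A share λ of those values is lost irrespective of their height: λ = 0.5 for (a), λ = 1 for (b).

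**Formulas, in units of s on the log scale.**
- Mean log after deletion: −λφ(z)/(1 − λp)
- Median after deletion: Φ⁻¹((1 − λp)/2), valid while this point lies below the limit
- Mean log after substitution at the limit: λ(−φ(z) + zp)
- Median after substitution: unchanged while fewer than half of the values exceed the limit

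**Numbers for p = 0.10.**
- (a) Deletion: −0.5 × 0.1755/0.95 = −0.0924; median Φ⁻¹(0.475) = −0.0627. Substitution: 0.5 × (−0.1755 + 0.1282) = −0.0237.
- (b) Deletion: −0.1755/0.90 = −0.1950; median Φ⁻¹(0.45) = −0.1257. Substitution: −0.1755 + 0.1282 = −0.0473.

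The bias is exp(s × shift) − 1:

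| Case | s | Geometric mean, deleted | Median, deleted | Geometric mean, at limit | Median, at limit |
|---|---|---|---|---|---|
| (a) half lost | 0.3 | −2.7% | −1.9% | −0.7% | 0 |
| (a) half lost | 0.5 | −4.5% | −3.1% | −1.2% | 0 |
| (a) half lost | 0.8 | −7.1% | −4.9% | −1.9% | 0 |
| (b) all lost | 0.5 | −9.3% | −6.1% | n/a | n/a |
| (b) all lost | 0.8 | −14.4% | −9.6% | n/a | n/a |
| (b) all lost | 1.0 | −17.7% | −11.8% | n/a | n/a |

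Substitution is marked n/a in (b) because no ULOQ is available there to substitute.

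**Simulation check.** With 20 per arm, 40,000 replicates, CV 50% (s = √ln 1.25 = 0.47) and 10% above the limit, the bias in mean, geometric mean and median was −5.7%, −4.3% and −3.1% with about half lost, and −12.1%, −8.9% and −6.1% with all lost. Adding the half-LLOQ rule for 10% BLQ values to full exclusion did not offset this: −13.8%, −13.3% and −6.1%.

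**Where the gain ends.** In (a) with p = 0.60 (z = −0.2533, φ = 0.3863), deletion shifts the mean log by −0.5 × 0.3863/0.70 = −0.276 and substitution by 0.5 × (−0.3863 − 0.1520) = −0.269, which is almost the same. At p = 0.70 (z = −0.5244, φ = 0.3477) the order reverses: −0.267 against −0.357.

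**The case against.** The strongest defence is that the exclusion is deliberate. When a sample was run at a low dilution, its ULOQ may sit below values quantified in other samples, and substituting it would rank a result of unknown height beneath them. The SAP's parenthesis points to this purpose. The difficulty is real, but the sample's own ULOQ is still a valid lower bound, and case (a) shows less bias with it than with deletion while well under half of the values exceed the limit.

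Other objections stand and limit the point:

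- A reader might infer that the highest results are always removed. In case (a) they are not, because quantified values above that ULOQ stay in.
- A reader might apply the case (b) losses generally, or take the larger ones for 20% ALQ (24% for the geometric mean and 18% for the median at log-SD 0.8). These need full deletion above one limit, which fits only the no-ULOQ case, and nothing shows that this case would arise.
- A reader might infer that deletion makes an arm look better. The marker definitions are not in the available text, so whether high is unfavourable is unknown, and SAP 7.9.2 plans no arm contrast.
- The data are descriptive, the programme was discontinued, and no participant finished 8 weeks. The exclusion branch may never be used.

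**Conclusion.** The point holds in a limited form. The final SAP contains a value-dependent exclusion at the high end only, and no other section corrects it. The direction follows from the rule: in expectation the mean, geometric mean, median and quartiles are low whenever the branch is used.

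The size cannot be derived from the documents. With 10% of values above the limit, reasonable assumptions give 3-7% for the geometric mean and 2-5% for the median under mixed dilutions, and 9-18% and 6-12% if no ULOQ exists. These figures assume log-normality and, for mixed dilutions, that half of the high values are lost irrespective of their height. No conclusion about efficacy or safety turns on this. It is worth changing because the correction is cheap and the loss would otherwise be invisible in the tables.

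**What to change.** Replace the last sentence of the ALQ rule in SAP 6.6.6:

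- Keep each ALQ result at the ULOQ that applied to that sample, flagged as a lower bound.
- If no ULOQ is available, keep the result as flagged and right-censored, ranked above the median for the median and quartiles. That ranking is itself an assumption, and an upper quartile that falls among censored results should be shown as a lower bound or not estimable. If the largest quantified value is used for the mean or geometric mean, label it a convention: the sample's own unknown limit may be lower, so it is not a lower bound.

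In the SAP 7.9.2 tables, add the number of ALQ and BLQ results per arm and visit, and state that markers with ALQ results are read from the median and quartiles already planned.

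The cost is a revised sentence or two and one row of counts. The downside is that means and geometric means with ULOQ substitution remain somewhat low (about 1% for the geometric mean in case (a) at log-SD 0.5). With mixed dilutions the gain over deletion disappears once more than about half of a marker's values exceed the limit; such a marker is better reported as the proportion above the limit.

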6.7 BASELINE, TIME WINDOWS AND CALCULATED VISITS

Regarding efficacy and safety endpoints, the term "baseline" refers to the last observed measurement prior to administration of any study medication.

Measurements taken prior to the first intake of study medication will be considered pretreatment values. Pre-treatment values will be assigned to a visit according to the nominal visit number as recorded on the eCRF or as provided by the laboratory.

In general, the date of the first drug administration will be used to separate pre-treatment from on-treatment values. Measurements taken after first trial medication intake will be considered on-treatment values if they have been obtained up to end of the parameter specific follow-up period as defined in Table 6.7:1 below and will be assigned to the corresponding study medication for efficacy and safety analyses.

c43185880-01

Proprietary confidential information © 2024 Boehringer Ingelheim International GmbH or one or more of its affiliated companies.

Measurements taken after the end of the endpoint specific follow-up period will be considered post-treatment values.

Endpoint	Last day of assignment to treatment phase (days after study medication stop date)
Efficacy	
HVPG	8 (REP + 1)
Fibroscan data	8
Biomarkers	1
Safety	
Adverse events	7
Safety laboratory measurements	3
Vital signs (including body weight, blood pressure)	1

 Table 6.7: 1
 Parameter specific follow-up period for the assignment to treatment phase

For derivation of the last value on treatment, minimum value on treatment, and maximum value on treatment, all values from the relevant phase (whether or not collected in any time window; see Table 6.1:1 for definition of the trial phases) will be considered; these will be derived for analysis of laboratory and vital signs data. For identification of potentially clinically significant abnormal laboratory values, all values (whether selected in any time window) up to 7 days after last treatment intake will be considered.

On-treatment efficacy, safety and biomarker measurements will be assigned to visits based on the extended time windows around the planned visit dates, defined relative to the day of first trial medication intake (see Table 6.7:2).

c43185880-01

Proprietary confidential information © 2024 Boehringer Ingelheim International GmbH or one or more of its affiliated companies.

Visit		Dlannad	Time window (Days)				
number	Visit label	day	Window	Start	End	Start	End
/name	v isit idoci	uay	(per CTP)	(per CTP)	(per CTP)	(extended)*	(extended)*
V1	Screening	-28				-∞-	0
			On-ti	reatment			
V2	Week 0	Day 1	N/A	1	1	≤ 1	1
V3	Week 1	Day 8	+2	8	10	2	11
V4	Week 2	Day 15	[contact]
V5	Week 4	Day 29	[contact]
V6	Week 6	Day 43	± 3	40	46	37	50
V7	Week 8/ EoT	Day 57	±5	52	62	51	Study medication stop date + X [#] days
			Off-t	reatment			
V8	Week 10/ EoS	Day 71	±5	66	76	Study medication stop date + X [#] days +1	Day of last follow-up value

T 11 (7)	TT' ' 1	c ·		• •.	C 1	1 *
I able 6 $/ \cdot /$	I ime windows	for assign	ment of measure	ments to visits	for statistical	analysis
1 4010 0.7.2		ioi ussign	ment of measure		101 Statistical	unuryono

Days are counted relative to the day of first treatment, which is defined as Day 1.

* Start (extended): End of extended window of last visit+1

End (extended): Midpoint of planned days between current visit and next visit

X= 3 days for safety laboratory; X=1 day for biomarkers and vital sign, respectively; X= 8 days (REP +1) for HVPG and fibroscan data.

The midpoint between two on-treatment visits defines the end of a time window, with the midpoint being included in the time window of the preceding visit. The end of the time window of the last on-treatment visit (end of treatment (EoT)) is endpoint dependent (Table 6.7:1).

Repeated and unscheduled efficacy and safety measurements will be assigned to the nominal visits and listed in the subject data listing according to the time windows described above. Only one observation per time window will be selected for analysis at an on-treatment visit - the value which is closest to the protocol planned visit day will be selected. If there are two observations which have the same difference in days to the planned day, the first value will be selected. If there are two observations on the same day, the first value will be selected. If there are multiple values within the time window of the last visit, including a value on the last day of drug intake, the value on the last day of drug intake is used as the value of the last visit.

Data prior to Day 1 of trial medication will be based on nominal visits and time windowing will not be applied. For these time points, data from the scheduled visit will always be selected if they are collected correctly. Unscheduled visits will only be considered if no correct data from the scheduled visit is available. If no correct data from a scheduled visit is

Proprietary confidential information © 2024 Boehringer Ingelheim International GmbH or one or more of its affiliated companies.

available and multiple unscheduled correct values are available for a visit, the first correct value will be selected.

7 PLANNED ANALYSIS

The format of the listings and tables will follow the BI guideline "Standards for Reporting of Clinical Trials and Project Summaries" (9.3).

Disposition of the patient population participating in the trial will be summarized by the presentation of the frequency of patients screened, screened but not entered, entered and treated, entered but not treated, who completed Week 8 visit (V7), who were prematurely discontinued treatment by reason, who completed the study, and who prematurely discontinued study.

A frequency of patients with iPDs will be presented by treatment group for TS. The frequency of patients in different analysis sets will also be presented for each treatment group. The iPDs per patient will be listed indicating whether the iPD led to exclusion from patient sets analyzed.

For tables presenting descriptive analysis of the endpoints and other variables, the set of summary statistics are:

N (number of patients with non-missing values) / Mean / SD / Min / Q1 (lower quartile) / Median / Q3 (upper quartile) / Max.

Statistical parameters will be displayed to a defined number of decimal places as specified in the BI guideline "Reporting of Clinical Trials and Project Summaries" (9.3).

Tabulations of frequencies for categorical data will include all possible categories and will display the number of observations in a category as well as percentage (%) relative to the respective treatment group. Percentages will be based on all patients in the respective patient set whether they have non-missing values or not. Percentages will be rounded to one decimal place. The category missing will be displayed if and only if there are actual missing values.

For PK analyte concentrations, as well as PK parameters, the following descriptive statistics will additionally be calculated:

- CV arithmetic coefficient of variation
- gMean geometric mean
- gCV geometric coefficient of variation
- P10 10th percentile
- Q1 1st quartile
- Q3 3rd quartile
- P90 90th percentile

The data format for descriptive statistics of plasma concentrations will be identical with the data format of the respective concentrations. The descriptive statistics of PK parameters will be calculated using the individual values with the number of decimal places as provided by

Proprietary confidential information © 2024 Boehringer Ingelheim International GmbH or one or more of its affiliated companies.

the evaluation program. Then the individual values as well as the descriptive statistics will be reported with three significant digits.

